7.2.1.5. Transitioning off Study Prandial Insulin Therapy

Patients will take their last prandial dose of study insulin (LY900014 or insulin lispro) at Visit 18 with the MMTT if performed the on same date as Visit 18 or in the evening the day prior to Visit 18 if the MMTT is performed prior to Visit 18 or at early discontinuation.

7.6 Treatment Compliance

Patients who, in the opinion of the investigator, are deemed consistently noncompliant may be discontinued from IP or from the study.

8.1.1. Permanent Discontinuation from Study Treatment

- If the patient, for any reason, requires treatment with another therapeutic regimen ~~(including a change to the prescribed basal insulin injection time for insulin glargine U-100) or therapeutic agent (including addition of a second basal insulin injection)~~ that has been demonstrated to be effective for treatment of the study indication. Discontinuation from IP should occur prior to introduction of the new agent.

9.1.4.4 Mixed-Meal Tolerance Test

~~Patients should arrive with no episodes of hypoglycemia (symptoms or BG \leq 70 mg/dL [3.9 mmol/L]) during this fasting period.~~

Target FBG prior to the MMTT: Patients must have an FBG range of 71 to 180 mg/dL (3.9-10.0 mmol/L) prior to starting the MMTT. If the glucose is outside of this range, the MMTT should be rescheduled.

In order to increase the likelihood of having patients arrive the morning of the MMTT within the target FBG range, please note the following:

- Patients should be instructed to avoid major changes in dietary intake or physical activity during the 3 days prior to the MMTT.
- Patients should be instructed to inject basal insulin according to their usual schedule
- Patients should not administer correction doses with insulin lispro or LY900014 within 4 hours of the start of the MMTT.
- During the 8 hour fasting period and up to 2 hours prior to the start of the MMTT, episodes of non-severe hypoglycemia (symptoms or BG \leq 70 mg/dL [3.9 mmol/L]) can be treated with 15 to -20 grams of carbohydrate. If a hypoglycemic episode requires more than approximately 20 grams of carbohydrate within 8 hours of the start of the MMTT or the patient experiences a severe hypoglycemic episode (as defined in Section 9.4.1 and 9.4.2), the patient should be instructed to notify the site and the MMTT must be rescheduled.

Insulin Injection:

~~Patients should inject basal insulin according to their usual schedule.~~

10.3.1 General Statistical Considerations

Efficacy analyses will be conducted on all randomized patients ~~using an intention to treat (ITT) approach~~ according to the treatment the patients are assigned.

~~The primary analysis method will be a~~ restricted maximum likelihood -based, mixed-effect model repeated measure (MMRM) analysis ~~using~~ will be used to analyze continuous longitudinal variables. All the longitudinal observations at each scheduled postbaseline visit— will be included in the analysis.

An analysis of covariance (ANCOVA) ~~model~~ will also be used to analyze continuous variables. The model for the change from baseline to the Week 26 HbA1c endpoint will include with treatment and strata (pooled country, type of basal insulin, and number of prandial doses at entry), and treatment as fixed effects and baseline as a covariate, will be conducted as supportive analyses. Unless otherwise stated, Missing-missing endpoints will be imputed using the last-observation-carried-forward (LOCF) approach, using only postbaseline data.

10.3.3.1 Primary Analyses

There will be 2 primary analysis methods, each tested at the full significance level of 0.05.

CCI ~~the primary analysis method will use the copy reference approach to impute missing data based on multiple imputations with a pattern mixture model. This analysis is for the ITT estimand (treatment regimen estimand) that will include all data collected from randomization through Week 26, regardless of IP use. The reference will be all observed data from the randomized patients in the same treatment group who discontinue IP and complete the study without missing data. After imputation, the primary efficacy comparison will be based on the contrast between LY900014 and insulin lispro from the ANCOVA analysis of change from baseline to Week 26 in HbA1c using all randomized patients as described in Section 10.3.1~~

If there are only a limited number of patients in the reference group as described above that leads to a failure in performing the proposed multiple imputation analysis, the reference will be changed to include all observed data from all randomized patients in the same treatment arm who complete the study without missing data.

CCI ~~the primary efficacy comparison will be based on the contrast between LY900014 and insulin lispro at Week 26 (Visit 18) from the MMRM analysis of change from baseline in HbA1c including data collected from all randomized patients prior to permanent discontinuation of IP through Week 26 (efficacy estimand). The analysis model and selection of covariance structure is described in Section 10.3.1.~~

For both primary analysis approaches, LY900014 will be declared noninferior to insulin lispro if the upper limit of the 2-sided 95% CI for the LS mean difference in the change from baseline in HbA1c for LY900014 minus insulin lispro is below +0.4%. In addition, the 95% CI for the

treatment difference will be compared to an alternative NIM of +0.3%. Both estimands will be tested at the full significance level of 0.05.

In addition to the primary objective, the superiority of LY900014 in controlling HbA1c compared to insulin lispro will also be assessed for each analysis approach described above. If the p-value is less than the alpha level from the graphical approach allocated to the superiority hypothesis, LY900014 will be declared superior to insulin lispro.

~~estimands to compare treatment groups for the analysis of the primary measure of change from baseline to Week 26 in HbA1c. One primary estimand will be an efficacy estimand that includes only data collected prior to permanent discontinuation of IP. CCI~~

~~Both estimands will use the same primary analysis model, and each will be tested at the full significance level of 0.05.~~

~~The primary efficacy comparison will be based on the contrast between LY900014 and insulin lispro at Week 26 (Visit 18) from the MMRM analysis of change from baseline in HbA1c using all randomized patients. If the upper limit of the 2-sided 95% CI for the LS mean difference in the change from baseline in HbA1c for LY900014 minus insulin lispro is below +0.4%, LY900014 will be declared noninferior to insulin lispro. In addition, the 95% CI for the treatment difference from the MMRM model will be compared to an alternative NIM of +0.3%. The analysis model and selection of covariance structure is described in Section 10.3.1~~

10.3.3.1.1. Sensitivity Analyses for Missing Data

For the ITT estimand, the reference group will be as described for the CCI primary analysis, and ANCOVA on the change from baseline to Week 26 in HbA1c will be used. For the efficacy estimand, the reference group will be the insulin lispro treatment group. Imputation will be for all longitudinal visits.

10.3.3.1.2. Additional Analyses for the Primary Endpoint

~~The primary analysis model, MMRM analysis model, will be repeated using the PP and Completer populations to check the sensitivity of the analysis. If the conclusion differs from that of all randomized patients, the data and analyses will be further investigated.~~

~~A secondary analysis model for the efficacy estimand will be an ANCOVA for HbA1c change from baseline to Week 26 (Visit 18), using the model described in Section 10.3.1. Missing endpoints will be imputed using the LOCF approach using postbaseline data only.~~

~~In addition to the primary objective, the superiority of LY900014 in controlling HbA1c compared to insulin lispro will also be assessed with the same model using all randomized patients. If the p-value is less than the alpha level from the graphical approach allocated to this subject hypothesis, LY900014 will be declared superior to insulin lispro.~~

10.3.3.2. Secondary Analyses

Analyses will be performed for both the efficacy estimand and ITT estimand as described in Section 10.3.3.1 using the same graphical testing scheme.

The graphical testing scheme will be described in the SAP. The study total alpha level (or study-wise type I error) is preset to be 5% for each estimand. The study total alpha level will be used for the primary objective in the initial step. The alpha level will be allocated to other key endpoints based on the weights in testing paths once the primary endpoint is successfully demonstrated. If 1 of the remaining hypotheses is successfully demonstrated with the preserved alpha level, its preserved alpha will be allocated to the remainder of the hypotheses by the weights in the paths. The iterative test procedure continues until none of the remaining hypotheses can be demonstrated with their preserved alphas or all hypotheses are demonstrated successful.

Superiority in change from baseline in HbA1c for LY900014 compared with insulin lispro will be determined from the analysis approaches outlined in Section 10.3.3.1.

HbA1c and change from baseline in HbA1c at all time points will be analyzed by the same MMRM model used for the primary analysis for the efficacy estimand.

Additional continuous secondary efficacy variables, as well as the change from baseline for these variables, will be analyzed either by the MMRM or ANCOVA models described in Section 10.3.1 for the efficacy estimand.

10.3.5.2. Subgroup Analyses

- Prandial insulin dosing plan (carbohydrate counting, ~~or fixed insulin dose~~ pattern adjustment)
- Type of basal insulin during the lead-in period (glargine, U-100, degludec-U-100 ~~or U-200~~)

Appendix 8

Eligibility for Insulin Lispro Antibody Follow-Up Assessment

Study visits will continue at approximately 3 month intervals for a maximum of ~~4-year~~ 6 months (approximately ~~48-26~~ weeks) after Visit 801 or until insulin lispro antibodies return to baseline range, whichever occurs sooner.

Visit 802 should occur no sooner than ~~9-13~~ weeks after Visit 801 to allow time to perform antibody testing on the Visit 801 sample.

In any case, even where insulin antibodies persist, the insulin lispro antibody follow-up assessment is expected to last no longer than ~~52-30~~ weeks from the protocol-scheduled last treatment visit.

Procedures for Insulin Lispro Antibody Follow-Up Assessment

Blood samples for insulin lispro antibody and HbA1c measurements should be collected at approximately 3-month intervals for up to ~~48~~26 weeks after Visit 801.

Schedule of Activities during Insulin Lispro Antibody Follow-Up Assessment

Study Period	Insulin Lispro Antibody Follow-Up Period				ED-IA Follow-Up
	802	803	804	805	
eCRF Visit Number	802	803	804	805	
Visit Window (days)	±14	±14	±14	±14	
Time on Study Relative to Last Treatment Dose Visit (weeks)	13 17	26 30	39	52	
Time on Study Relative to First Treatment Dose Visit (weeks)	30 43	52 56	65	78	
IWRS	X	X	✗	✗	X
Dispense glucose monitoring and ancillary supplies	X	✗	✗		
Telephone call for visit reminder or informing patient of completion in the study	X	X	✗		
Return of unused diabetes medications and study supplies if required by local regulations	X	X	✗	✗	X
Clinical Assessments					
Concomitant medication (including OAMs)	X	X	✗	✗	X
Total daily prandial insulin dose	X	X	✗	✗	X
Total daily basal insulin dose	X	X	✗	✗	X
Vital signs	X	X	✗	✗	X
Body weight	X	X	✗	✗	X
Adverse events	X	X	✗	✗	X
Laboratory Assessments					
Anti-insulin lispro antibodies	X	X	✗	✗	X ^a
HbA1c	X	X	✗	✗	X

Leo Document ID = 8db592ec-e163-4881-bfaa-037bdb0f26df

Approver: PPD [REDACTED]
Approval Date & Time: 19-May-2017 19:06:29 GMT
Signature meaning: Approved

Approver: PPD [REDACTED]
Approval Date & Time: 19-May-2017 20:49:25 GMT
Signature meaning: Approved

Figure 5.1.	Illustration of study design.	12
Figure 6.1.	Testing scheme for primary and multiplicity adjusted objectives.	28

Table of Contents

Appendix		Page
Appendix 1.	Empirical Estimation of Relative Event Rate	49
Appendix 2.	Statistical Analysis for Japan	51
Appendix 3.	Statistical Analysis for Maximum Extended Enrollment (MEE) Addendum ...	52

3. Revision History

Statistical analysis Plan (SAP) Version 1 was approved prior to the first patient visit on 7 July 2017. Version 1 was based on the Protocol I8B-MC-ITRN (ITRN) approved on 17 February 2017 and amended on 19 May 2017.

The second version was approved on 27 March 2018. The main changes are listed below:

- adding analysis details (for example, analysis population or period, on investigational product (IP) data versus all data regardless of IP use), derivations (for example, derivations for 10-point self-monitored blood glucose [SMBG]-related and insulin dose-related variables), and rules (for example, to define unique hypoglycemia events)
- modifying analysis input data scope: for the continuous analysis of last observation of clinical laboratory tests, unplanned tests are excluded from analysis to reduce bias (Computational Science Symposium Development of Standard Scripts and Programming Working Group 2013 [WWW])
- deleting the following analyses:
 - treatment-emergent adverse events (TEAE) by Preferred Term (PT) summary using all data regardless of IP use, because the by System Organ Class (SOC) summary and the common TEAE summary together are sufficient
 - notable TEAE summary using on IP data, because the summary using all data regardless of IP use and the summary of its drug-related subset are more clinically relevant
 - malignant neoplasm TEAE summary, due to the expected low incidence rate; the analysis will be performed at the compound or integration level
 - hypoglycemia summaries for postmeal hypoglycemia <54 mg/dL, because they are expected to be few thus less clinically relevant compared with other types of hypoglycemia events planned for analysis
 - hypoglycemia summaries for postmeal all documented and documented unspecified hypoglycemia because the information of time relative to meal is missing for documented unspecified hypoglycemia events

This SAP is the third version approved prior to the first unblinding. The main changes are listed below:

- replacing the imputation method with **CCI** “return to baseline” imputation method when the number of patients who discontinued IP but complete the study procedure without missing data is very limited
- updating the transition weights in the graphical testing scheme based on the results from Phase 1b studies (I8B-FW-ITRH and I8B-MC-ITRW)

- adding the on IP definition for mixed-meal tolerance test (MMTT) for which the 14-day rule is not applicable
- removing vital sign analyses except weight analysis for the lead-in period
- adding analysis details (for example, defining the pooled country used in the statistical modeling and region for subgroup analyses) and removing contradictory statements
- clarifying the analysis of important protocol deviations when duplicates occur

4. Study Objectives

Table 4.1 shows the objectives and endpoints of the study.

Table 4.1. Objectives and Endpoints

Objectives	Endpoints
Primary Objective	
1. (H1) To test the hypothesis that LY900014 is noninferior to insulin lispro on glycemic control (NIM=0.4% for HbA1c) in patients with T2D, when administered as prandial insulin (0 to 2 minutes prior to the meal), in combination with basal insulin glargine or insulin degludec for 26 weeks	1. Difference between LY900014 and insulin lispro in change from baseline to Week 26 in HbA1c
Multiplicity Adjusted Objectives	
2. (H2) To test the hypothesis that LY900014 is superior to insulin lispro in controlling 1-hour PPG excursions, when administered as prandial insulin	2. Difference between LY900014 and insulin lispro in the 1-hour PPG excursion (serum glucose measured 1 hour after the start of the meal minus fasting serum glucose) from an MMTT at Week 26
3. (H3) To test the hypothesis that LY900014 is superior to insulin lispro in controlling 2-hour PPG excursions when administered as prandial insulin	3. Difference between LY900014 and insulin lispro in the 2-hour PPG excursion (serum glucose measured 2 hours after the start of the meal minus fasting serum glucose) from an MMTT test at Week 26
4. (H4) To test the hypothesis that LY900014 is superior to insulin lispro on improving glycemic control (HbA1c) when administered as prandial insulin	4. Difference between LY900014 and insulin lispro in change from baseline to Week 26 in HbA1c
Other Secondary Objectives	
5. To compare LY900014 and insulin lispro with respect to the rate of severe hypoglycemic events	5. Rate (events/patient/100 years) of severe hypoglycemic events from baseline through Week 26
6. To compare LY900014 and insulin lispro with respect to the incidence and rate of documented symptomatic postmeal hypoglycemia	6. Rate (events/patient/year and/or events/patient/30 days) and incidence (percent of patients with at least 1 event) of documented symptomatic postmeal hypoglycemia within 1 and 2 hours after start of a meal from baseline through Week 26
7. To compare LY900014 and insulin lispro with respect to the incidence and rate of documented symptomatic hypoglycemia	7. Rate (events/patient/year and/or events/patient/30 days) and incidence (percent of patients with at least 1 event) of documented symptomatic hypoglycemic events from baseline through Week 26
8. To compare LY900014 and insulin lispro with respect to 1,5-AG	8. Change from baseline 1,5-AG values at Week 26
9. To compare LY900014 and insulin lispro with respect to 10-point SMBG profiles	9. Change from baseline 10-point SMBG values at Week 26

Objectives and Endpoints

Objectives	Endpoints
Other Secondary Objectives (Continued)	
10. To compare LY900014 and insulin lispro with respect to total, basal, and prandial insulin dose	10. Change from baseline in total, basal and prandial insulin dose and prandial/total insulin dose ratio at Week 26
11. To compare LY900014 and insulin lispro with respect to diabetes treatment satisfaction as measured by the ITSQ	11. Change from baseline ITSQ regimen inconvenience and lifestyle flexibility domain scores at Week 26
12. To compare LY900014 and insulin lispro with respect to the proportion of patients achieving HbA1c targets	12. The proportion of patients with HbA1c <7% and ≤6.5% at Week 26
Tertiary/Exploratory Objectives	
13. To compare the safety of LY900014 relative to insulin lispro	13. Adverse events, vital signs, chemistry, and hematology laboratory measures
14. To compare the incidence of treatment-emergent anti-insulin lispro antibodies for LY900014 and insulin lispro	14. Incidence of treatment-emergent positive anti-insulin lispro antibodies
15. To compare LY900014 and insulin lispro with respect to quality of life as measured by the EQ-5D-5L	15. Change from baseline in EQ-5D-5L UK-population based health state index score and EQ-VAS score at Week 26
16. To compare LY900014 and insulin lispro with respect to the impact that diabetes has on the ability to work and perform regular activities as measured by the WPAI-GH	16. Change from baseline in WPAI-GH item scores at Week 26
17. To compare LY900014 and insulin lispro with respect to changes in body weight	17. Change from baseline to Week 26 in weight (kg)
18. To compare LY900014 and insulin lispro with respect to the proportion of patients achieving improvement from baseline HbA1c targets	18. The proportion of patients with shifts in HbA1c to <8% and ≤9%, and >9% from baseline to Week 26
19. To compare LY900014 and insulin lispro with respect to glycemic variability	19. Within-day and between-day glycemic variability measured by the standard deviation and the coefficient of variation of 10-point SMBG profiles

Abbreviations: 1,5-AG = 1,5-Anhydroglucitol; EQ-5D-5L = European Quality of Life – 5 Dimensions 5 Level; EQ-VAS = EuroQol visual analog scale; HbA1c = hemoglobin A1c; ITSQ = Insulin Treatment Satisfaction Questionnaire; MMTT = mixed-meal tolerance test; NIM = noninferiority margin; PPG = postprandial glucose; SMBG = self-monitored blood glucose; T2D = type 2 diabetes; WPAI-GH = Work Productivity and Activity Impairment Questionnaire General Health.

5. Study Design

[figure not shown]

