7.8.2. Special Treatment Considerations

After discontinuation of IP at the end of the treatment period or earlier, randomized patients should restart the prandial insulin used prior to study entry or transition to a rapid-acting insulin analog other than insulin lispro if the patient was not treated with insulin lispro prestudy. Patients may continue treatment with the basal insulin used during the study or return to their prestudy basal insulin at investigator discretion.

Please also refer to [Appendix 8](#) for information regarding the insulin lispro antibody follow-up assessment. During this follow-up period, OAMs used during the study treatment period should be continued and other prestudy OAMs may be considered at investigator discretion as appropriate.

Investigators should provide patients with appropriate guidance for glucose monitoring and insulin dose adjustment throughout the follow-up period in order to maintain glycemic control.

8. Discontinuation Criteria

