6.12.2. Adverse Events

Analyses of AEs will include 2 sets of analyses, unless otherwise specified. The first set of analyses will include data collected prior to permanent discontinuation of IP. The second set of analyses will include all data collected during the course of the entire study including the follow-up visit, regardless of IP use.

Events that are newly reported after the first dose of prandial insulin provided as study drug (that is, open-label insulin lispro used during the lead-in period or IP used during the treatment period) or reported to worsen in severity from baseline (defined in [Table 6.2](#) for a specific study period) will be considered TEAEs. The MedDRA Lowest Level Term (LLT) will be used in the treatment-emergent assessment. The maximum severity for each LLT during the baseline period will be used as baseline severity. For events occurring on the day of first dose of bolus insulin provided by this study, the case report form (CRF)-collected flag will be used to determine whether the event started or worsened post-treatment.

In an overview table, the number and percentage of patients who experienced a TEAE, experienced serious adverse event (SAE), died due to an AE, discontinued from study due to an AE, or discontinued IP due to an AE will be summarized by treatment group .

The number and percentage of patients with TEAEs will be summarized by treatment using MedDRA PT nested within SOC. Events will be ordered by decreasing frequency within SOC. As an additional table, the percentages of patients with TEAEs will be summarized by treatment using MedDRA PT (without regard to SOC). Events will be ordered by decreasing frequency. Statistical comparisons will be applied at both the SOC and PT levels. Fisher's exact test will be performed for treatment comparison.

The number and percentage of patients with TEAEs by maximum severity will be summarized by treatment using MedDRA PT (regardless of SOC) and data collected prior to permanent discontinuation of IP. For each patient and TEAE, the maximum severity for the MedDRA PT is the maximum postbaseline severity observed from all associated LLTs mapping to the MedDRA PT. No statistical comparison between treatment groups will be conducted.

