The number and percentage of patients with common TEAEs (defined as $\geq 5\%$ before rounding for LY900014-treated patients) will be summarized by treatment group using MedDRA PT (without regard to SOC). Events will be ordered by decreasing frequency. Treatment will be compared by Fisher's exact test.

The number and percentage of patients who experienced an SAE including deaths and SAEs temporally associated or preceding deaths will be summarized by treatment group using MedDRA PT regardless of SOC. Events will be ordered by decreasing frequency. A listing of all SAEs will also be provided.

The number and percentage of patients who discontinued from study due to an AE will be summarized by treatment group using MedDRA (without regard to SOC) using all data regardless of IP use. The number and percentage of patients who discontinued IP due to an AE will be also summarized by treatment group using MedDRA PT (without regard to SOC) using data prior to permanent discontinuation of IP. Events will be ordered by decreasing frequency. A listing of all AEs as reason for study or IP discontinuation will also be provided.

The number and percentage of patients who experienced other notable TEAEs (potential systemic hypersensitivity reaction, injection site reaction, and hepatic disorder) will be summarized by treatment group using all TEAEs regardless of IP use. For events that are gender-specific (as defined by MedDRA), the denominator and computation of the percentage will include only patients from the given gender.

Table 6.5 summarizes the planned analyses and the requirement of analysis data for different analysis periods. A 'Yes' in the IP USE column indicates that only data collected prior to permanent discontinuation of IP will be included.

Table 6.5. Treatment-Emergent Adverse Event Analysis Periods

Analysis Period	Analysis Population	Analysis	IP USE	Treatment
Lead-in Period	All enrolled patients	AE overview; TEAE by PT; SAE, discontinuation due to AE	N/A	Open-label insulin lispro
Treatment Period (0-26 Weeks)	All patients in safety population	AE overview; TEAE by SOC and by PT; common TEAE; TEAEs by maximum severity; SAE; IP discontinuation due to AE	Yes	LY900014, insulin lispro
Week 0 – Visit 801	All patients in safety population	AE overview; TEAE by SOC; common TEAE; SAE; other notable AEs; study discontinuation due to AE	All data regardless of IP use	LY900014, insulin lispro

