6.12.4.2. Systemic Hypersensitivity Reaction

The number and proportion of patients experiencing treatment-emergent potential systemic hypersensitivity reactions will be summarized and compared by treatment group using Fisher's exact test. The following MedDRA SMQ will be used to identify potential systemic hypersensitivity reactions from all TEAEs:

- Anaphylactic reaction (SMQ). Besides using the narrow and broad terms designated within the SMQ, the following search algorithm will also be implemented as another approach to determine if a patient had an anaphylactic reaction: if a patient (had at least 1 event in Category A) or (had at least 1 event that is in category B and also had at least 1 event that is in category C) or (had at least 1 event that is in category D and [also had at least 1 event in category B or at least 1 event in category C])
- Angioedema (SMQ)
- Hypersensitivity (SMQ)

Specifically, need to perform the following: (1) any narrow or algorithmic term from any 1 of the 3 SMQs indicated above (that is, combined search across narrow and algorithmic portions of all 3 SMQs); (2) any narrow scope term within each SMQ, separately (that is, narrow SMQ search); (3) any term within each SMQ, separately (that is, broad SMQ search); (4) narrow scope term search within each SMQ, report the PT nested within each SMQ.

A similar summary will be provided for the TEAE related to study drug judged by investigator.

Note that an individual patient may contribute multiple events. Also, a single event may satisfy multiple SMQs, in which case the event contributes to every applicable SMQ.

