6.12.4.3. Injection Site Reaction

The injection site reactions will be searched by MedDRA PTs from all TEAEs. The number and percentage of patients experiencing treatment-emergent injection site reaction will be summarized and compared by treatment group using Fisher's exact test.

For injection site reactions identified by MedDRA PTs, the presence and severity of erythema, induration, pain, pruritus and edema (collected on the eCRF) will be summarized for each treatment. There will be no statistical comparison between treatments.

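### The only pooled comparison of injection site reactions uses all data through Visit 801, and no investigator-related or on-IP version is planned

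*SAP*

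**What the plan says.** SAP 6.12.2 plans two sets of adverse event analyses unless otherwise specified, one before permanent discontinuation of IP and one on all data. Protocol 10.3.1 says the same. The notable events (potential systemic hypersensitivity, injection site reaction, hepatic disorder) are an exception: they "will be summarized by treatment group using all TEAEs regardless of IP use".

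Table 6.5 agrees. Its Week 0 to Visit 801 row, on all data, lists "AE overview; TEAE by SOC; common TEAE; SAE; other notable AEs; study discontinuation due to AE". Its 0-26 week row, restricted to on-IP data, lists "AE overview; TEAE by SOC and by PT; common TEAE; TEAEs by maximum severity; SAE; IP discontinuation due to AE" and so has no notable events. For the preferred-term tables, 6.12.2 adds: "Statistical comparisons will be applied at both the SOC and PT levels", by Fisher's exact test.

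SAP 6.12.4.3 states: "The injection site reactions will be searched by MedDRA PTs from all TEAEs". It plans one Fisher comparison of patients with any such reaction, and an untested summary of local signs and their severity. SAP 6.12.4.2, on hypersensitivity, adds: "A similar summary will be provided for the TEAE related to study drug judged by investigator". Section 6.12.4.3 has no counterpart.

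The Revision History gives the reason for the arrangement. Version 2 removed the "notable TEAE summary using on IP data, because the summary using all data regardless of IP use and the summary of its drug-related subset" were considered clinically more relevant.

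After IP stops, Protocol 7.8.2 says that "randomized patients should restart the prandial insulin used prior to study entry or transition to a rapid-acting insulin analog other than insulin lispro" if they did not use lispro before the study.

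**The concern.** The stated reason for dropping the on-IP notable-event table is that two summaries remain: all data, and a drug-related subset. For injection site reactions the current plan contains only the first. The pooled count therefore mixes reactions under randomized treatment with reactions that arise later, mostly on nonstudy prandial insulin, and books both to the randomized arm. If the later reactions occur at a similar rate in both arms, they pull the risk ratio toward 1 and cost some power.

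Local tolerability is a product-specific question here. Protocol 3.2 describes treprostinil in LY900014 as an excipient that speeds absorption by local vasodilatation. The proportion of patients with any injection site reaction is the natural summary of that question, and it is the one that has neither an on-IP nor an investigator-related version.

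**Working it through.** **Step 1. Which comparisons are planned for injection site reactions?**

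| Comparison | Data | Pooled over terms? | Source |
|---|---|---|---|
| Each preferred term, Fisher | On IP, 0-26 weeks | No | SAP 6.12.2, Table 6.5 |
| Any injection site reaction, Fisher | All data to Visit 801 | Yes | SAP 6.12.4.3, 6.12.2, Table 6.5 |
| Logistic model with antibody-status subgroup and interaction | All data | Yes | SAP 6.12.7.1 |
| Any injection site reaction, investigator-related | Not planned | - | - |
| Any injection site reaction, on IP | Not planned | - | - |

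The plan states no figure on this point, so there is none to reproduce.

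**Step 2. How much of the window is off IP?** The documents give 26 weeks of treatment and 4 weeks of follow-up.
- A patient who completes treatment: 4/30 = 13.3%.
- Planned non-completers: 670 - 568 = 102, and 102/670 = 15.2%. If all of them stopped IP at week 13 (17 weeks off IP) and stayed in the study: (0.848 × 4 + 0.152 × 17)/30 = 19.9%. This is an upper-end assumption, because patients who leave the study contribute less off-IP time.

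**Step 3. Size of the dilution.** Assumptions, none of them from the documents: 26-week on-IP incidence of 6% on LY900014 and 2% on lispro; constant hazards; nonstudy insulin reacting at the lispro rate. There are 670/2 = 335 patients per arm. Power is from exact enumeration of the two-sided 0.05 Fisher test.

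With no early stops:
- On IP: 6.00% vs 2.00%; risk ratio 3.00; difference 4.00 points; power 0.72.
- All data, LY900014: 1 - 0.94 × 0.98^(4/26) = 6.29%.
- All data, lispro: 1 - 0.98^(30/26) = 2.30%.
- Risk ratio 6.29/2.30 = 2.73; difference 3.99 points; power 0.68.

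With a fraction d stopping IP at week 13 and staying, on-IP incidence is (1 - d)p + d[1 - (1 - p)^0.5], with p the 26-week incidence. The off-IP weeks are added as above:

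| d | Off-IP hazard relative to lispro | Risk ratio, on IP to all data | Difference (points) | Power |
|---|---|---|---|---|
| 0 | 1 | 3.00 to 2.73 | 4.00 to 3.99 | 0.72 to 0.68 |
| 0 | 2 | 3.00 to 2.52 | 4.00 to 3.98 | 0.72 to 0.64 |
| 15.2% | 1 | 3.00 to 2.60 | 3.70 to 3.69 | 0.68 to 0.62 |
| 20% | 1 | 3.00 to 2.56 | 3.61 to 3.59 | 0.67 to 0.60 |
| 20% | 2 | 3.00 to 2.28 | 3.61 to 3.58 | 0.67 to 0.54 |

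**Step 4. Lower rates.** Assume 3% vs 1% on IP and add 0.2% off-IP incidence to both arms. For comparison, four weeks at the lispro rate would be 1 - 0.99^(4/26) = 0.15%. The risk ratio goes from 3.00 to 2.67 and power from 46% to 42% (two-proportion power calculation), with the difference near 2.0 points. The pattern is the same.

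**The case against.** The strongest reply is that on-IP testing survives. A reader might infer that injection site reactions have no on-IP comparison at all. The documents do not support that: the on-IP preferred-term table counts patients and tests every term. What it cannot give is the proportion with any injection site reaction, since a patient may appear under several terms and sparse events are split.

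A reader might also infer that reactions counted off IP cannot come from the randomized product. That does not follow. SAP 6.1 classes an adverse event as on IP only up to one day after the last dose, so a delayed reaction to IP falls outside the cut. Keeping such events is a fair reason to retain the all-data table. Patients who used lispro before the study may also return to it.

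Nor is it clear that injection site reactions are the lone exception. SAP 6.12.4.4.1 calls its hepatic events drug-related but identifies them by standardized MedDRA queries and states no relatedness filter. Only hypersensitivity has an explicit investigator-judged subset.

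Further, basal insulin is injected throughout, so an on-IP cut alone does not isolate the study prandial insulin. This stands, and it makes the related subset the more useful addition.

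Finally, the deletion is recorded in a revision history, and a mismatch with such a log is not in itself an error. The point rests on the current 6.12.2, Table 6.5 and 6.12.4.3. The log matters only because it gives the sponsor's reason for the present arrangement.

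**Conclusion.** The point holds in limited form and is minor. Only the pooled patient-level analysis of injection site reactions is affected: it is planned on all data alone, and the drug-related companion on which the sponsor's reason relies is not specified for this category. The dilution is modest and appears on the ratio scale and in power, not in the risk difference. The risk ratio goes from 3.0 to about 2.7 and power from 0.72 to 0.68 in the no-early-stop case, with larger losses only if many patients stop IP and stay in the study or if nonstudy insulin reacts more often. These sizes rest on assumed reaction rates, constant hazards and equal off-IP rates in both arms. No primary or multiplicity-adjusted test is touched; the analysis serves exploratory objective 13.

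**What to change.** In SAP 6.12.4.3, add a pooled patient-level summary of injection site reactions judged related to study drug by the investigator, with Fisher's exact test, in parallel with 6.12.4.2. This is the main addition. Also add a pooled on-IP version with Fisher's exact test, using the date rule in SAP 6.1, and enter it in the 0-26 week row of Table 6.5. Enter the related summary in Table 6.5 as well, and keep the all-data comparison as planned.

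The cost is one or two tables. Protocol 9.2 already has investigators record relatedness for every adverse event, so no new data are needed. Two limits should be noted beside the tables: reactions reported more than one day after the last IP dose do not enter the on-IP version, and that version still includes reactions to basal insulin.
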